	➤ Cosmetic Outcomes CRF	Study Chair (or delegate) will: ➤ Evaluate photos ➤ Submit the Cosmetic Outcomes CRF via InForm

Table continued on next page.

Acronyms used in following table:

CRP = Clinical Research Professional (at enrolling site)

CSC = Central Study Coordinator (sits at lead site, Dana-Farber)

Timepoint	Data to be collected	Who's responsible? How to Collect & Submit data?
12-months[^] (defined as 12-months after initiation of PMRT)	➤ 12-month Patient Questionnaire	CSC should: ➤ Administer patient questionnaire ➤ Enter patient responses into InForm ➤ Send participant \$50 gift card
	➤ Reconstruction photographs	Patient or Clinician should: ➤ Take reconstruction photographs Patient or Clinician or Site CRP should: ➤ Send photographs to CSC electronically via secure file transfer protocol (FTP). Contact the CSC for detailed FTP instructions.
	➤ Cosmetic Outcomes CRF	Study Chair (or delegate) will: ➤ Evaluate photos ➤ Submit the Cosmetic Outcomes CRF via InForm
18-months (defined as 18-months after initiation of PMRT)	➤ 18-month Patient Questionnaire	CSC should: ➤ Administer patient questionnaire ➤ Enter patient responses into InForm ➤ Send participant \$50 gift card
	➤ Reconstruction photographs	Patient or Clinician should: ➤ Take reconstruction photographs Patient or Clinician or Site CRP should: ➤ Send photographs to CSC electronically via secure file transfer protocol (FTP). Contact the CSC for detailed FTP instructions.
	➤ Cosmetic Outcomes CRF	Study Chair (or delegate) will: ➤ Evaluate photos ➤ Submit the Cosmetic Outcomes CRF via InForm
Annual Follow up 1 of 10[^] (defined as 1-year after initiation of PMRT)	➤ Follow-up Medical Record Review CRF	Site CRP should: ➤ Submit electronically via InForm If no follow up data available in medical record, CSC may mail patient brief set of questions and/or call patient for follow up.
Annual Follow up 2 of 10 (defined as 2-years after initiation of PMRT)	➤ Follow-up Medical Record Review CRF	Site CRP should: ➤ Submit electronically via InForm If no follow up data available in medical record, CSC may mail patient brief set of questions and/or call patient for follow up.
At EACH: Annual Follow up 3, 4, 5, 6, 7, 8, 9, and 10 of 10	➤ Follow-up Medical Record Review CRF	Site CRP should: ➤ Submit electronically via InForm If no follow up data available in medical record, CSC may mail patient brief set of questions and/or call patient for follow up.

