10. STATISTICAL CONSIDERATIONS

10a. Accrual: Based on previous years' treatment records, we anticipate that there will be about 40-50 eligible patients per month across the multiple participating academic and community centers. The accrual rate of this study is expected to be about 22 patients per month. We expect conservatively (based on survey data) that 75% of the eligible patients (after confirmation of the need for radiation therapy) are willing to be randomized to either the long-course or short-course treatment. The accrual will be open until 400 patients are enrolled. Randomization will be stratified by treatment center and age of the patient (<45 vs. ≥45). We expect the proportion of patients in the younger cohort of the study sample to be 40%. The anticipated length of the accrual period is 21-27 months.

10b. Statistical analysis plan for patient-reported quality of life outcomes and power considerations

Quality of life (QoL) measurement and the primary endpoint: We will use an array of instruments to rigorously assess quality of life among study participants, such as the FACT-B scores, satisfaction with breast surgery outcomes (BREAST-Q), Lymph-ICF, and financial burden. We will record and report all reasons for dropout and which outcomes were not reported, and include this data in our final reports. FACT-B (version 4) specifically measures quality of life in breast cancer patients and includes modules for assessing physical well-being, emotional well-being, social well-being, functional well-being and a 2-item question characterizing a breast cancer patient's relationship with her physician. QoL will be assessed at baseline, 6 months, 12

months and 18 months. This data will allow peer reviewers and readers of our publications to assess the validity of our study.

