The primary analysis and power: We hypothesize that hypofractionated (short-course) radiation therapy has a higher reconstruction success rate, compared to the conventional fractionation (long-course) radiation at 18-months. We will use Chi-square test for 2x2 table to test this superiority hypothesis. We will also construct a two-sided 95% confidence interval for the difference in the composite outcome of reconstruction success likelihood (defined as no major complications, presence of reconstruction, and good or excellent cosmetic outcome). Recent estimates of reconstruction success after implant reconstruction and conventional radiation reveal a 71% likelihood at the 2-year time period.⁴⁶ “**Table: Effect size and power for superiority tests**” shows the available power with various reconstruction success probabilities for hypofractionation (short-course treatment), given the sample size of 400 patients. Variables that may affect outcomes such as chemotherapy regimen, endocrine therapy and patient age will be assessed for impact to ensure balance between both treatment arms.

Table: Effect size and power for superiority tests		
Reconstruction Success Likelihood (%)		Power (%)
Long-course radiation	Short-course radiation	
71.0	82.8	80
71.0	84.4	90

N=400 randomized patients and α (two-sided)=0.05

[figure not shown]
Data monitoring of local/regional recurrence event:

We will also follow oncologic outcomes to exclude any unexpected increase in the risk of recurrence with hypofractionation (short-course) radiation therapy, although a detectable increase in recurrence rates is unlikely given data from prior experiences of hypofractionation. The cumulative incidence of local or regional recurrence in a recent series of post-mastectomy

radiation therapy is about 2% at 18 months.³ Therefore, in the case where the recurrence rate is suggested to be statistically significantly greater than 2%, the study will be suspended to allow for investigation.

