Local/regional recurrence event rate monitoring will occur at the first meeting of the DF/HCC Data and Safety Monitoring Board (DSMB) and continue until the last patient has completed radiation. Data analysis will be performed every 6 months (see Section 11). Specifically, the event rate and corresponding 0.95 exact binomial confidence interval will be calculated, where the numerator is the number of the local/regional recurrence events and the denominator is the number of patients who have completed short-course treatment at time of analysis. The results will be reviewed by the DSMB. If the lower boundary of the 0.95 confidence interval is greater than 2%, accrual of the study will be suspended and a decision will be made as to whether accrual can be resumed or if the study should be closed by the study team in consultation with the DSMB, IRB and study advisory board. The boundary for this criterion is shown in “**Figure: Stopping boundary for local/regional recurrence-event monitoring**”. With the sample size of 200 in the short-course radiation arm, the probability that the interim data meet the stopping criteria (see figure) in the course of the trial is 72% if the true local or regional recurrence rate were 5%. It would be 98% if the true recurrence rate is 8% at 18-months.

Figure: Stopping boundary for local/regional recurrence-event monitoring

There has been no suggestion of increased rare radiation side-effects or mortality with hypofractionation (short-course) radiation therapy with long term follow up in the studies using hypofractionation.^{23,24,31} Therefore, we do not expect any increased risk of side-effects in our short-course arm. Nevertheless, to be extra cautious, we will follow these outcomes in our patients. We recognize that our study is too short to detect differences in long-term distant recurrence, cardiac mortality and overall mortality. Therefore, we will create an infrastructure with which monitor these outcomes and apply for additional funding for longer follow up.

10e. Heterogeneity in treatment (HTE) outcomes

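### The recurrence stopping rule sets patients with little follow-up against an 18-month benchmark, so the stated 72% and 98% stopping probabilities do not describe it

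*Combined protocol and SAP*

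**What the plan says.** Section 10c (data monitoring of local/regional recurrence) takes its limit from a published series in which the cumulative incidence after post-mastectomy "radiation therapy is about 2% at 18 months". Every 6 months an exact binomial 95% confidence interval is calculated. The numerator is the number of recurrences and "the denominator is the number of patients who have completed short-course treatment at time of analysis". If the lower limit exceeds 2%, "accrual of the study will be suspended and a decision will be made as to whether accrual can be resumed". Monitoring is to "continue until the last patient has completed radiation".

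For 200 short-course patients the section states that "the probability that the interim data meet the stopping criteria (see figure) in the course of the trial is 72" percent for a true rate of 5%, and then: "It would be 98% if the true recurrence rate is 8% at 18-months".

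Two other places bear on timing. Section 9.1 defines its own time point as "18-months (defined as 18-months after initiation of PMRT"). Section 10a says: "The anticipated length of the accrual period is 21-27 months".

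**The concern.** The limit is a risk over 18 months. The statistic is events so far divided by everyone treated so far. A patient who finished radiation the day before a look enters the denominator as if she had already passed 18 months without recurrence. Because the rule lapses at the last radiation treatment, most 18-month windows are still open when it last applies. The observed proportion is therefore diluted relative to the benchmark, and the chance of crossing the boundary should fall below that of a rule based on complete outcomes.

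This is the plan's only numerical boundary on the oncologic risk of the short course. A DSMB or IRB that relies on 72% and 98% could believe the trial is better protected than it is.

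**Working it through.** **Inputs from the plan.** Benchmark 2% at 18 months; lower limit of an exact 95% interval; 6-monthly looks; 200 short-course patients; end at last radiation (all Section 10c). Accrual 21-27 months, or 22 patients per month (Section 10a). Radiation may start up to 4 months after randomization (Section 5.2).

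**Assumptions not in the plan.** Uniform accrual; radiation start 1 month, or uniformly 0-4 months, after randomization; radiation lasting 0.75 month (short course) or 1.15 months (long course); looks from month 6 plus one at last radiation; constant recurrence hazard from radiation start.

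**Step 1: boundary.** The lower limit exceeds 2% at the smallest x with P(X ≥ x | n, 0.02) < 0.025. This gives 4/50, 6/100, 8/150 and 9/200.

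**Step 2: reproduce the stated figures.** Treat each patient as a Bernoulli outcome fully known when she enters the denominator, and compute the exact probability of crossing at any look.

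| Looks at n = | True 2% | True 5% | True 8% |
|---|---|---|---|
| 200 only | 2.0% | 67.3% | 98.2% |
| 50, 100, 150, 200 | 4.1% | 71.3% | 98.5% |
| 40, 80, 120, 160, 200 | 4.3% | 72.1% | 98.6% |

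The plan's 72% and 98% match this model.

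**Step 3: hand check of the rule as written.** Consider only the final look. With accrual over A months and the last patient finishing 0.75 month after starting, follow-up from radiation start is uniform on (0.75, A + 0.75), with mean A/2 + 0.75. A true 18-month risk F gives a monthly hazard λ = −ln(1 − F)/18, which is 0.00285 for 5% and 0.00463 for 8%. The expected proportion q is the average of 1 − exp(−λt) over that range.

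| A | Mean follow-up | Share at 18 months, (A + 0.75 − 18)/A | F | 200q | P(X ≥ 9) |
|---|---|---|---|---|---|
| 21 | 11.25 months | 18% | 5% | 6.3 | 18% |
| 21 | 11.25 months | 18% | 8% | 10.1 | 68% |
| 27 | 14.25 months | 36% | 5% | 7.9 | 39% |
| 27 | 14.25 months | 36% | 8% | 12.7 | 89% |

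Complete follow-up would give 10 and 16 expected events. With radiation delays of 0-4 months included, 17-40% of short-course patients have reached 18 months at the last short-course treatment.

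**Step 4: full simulation with all looks** (12,000 runs per scenario; ranges cover both delay patterns and ending at the last radiation in the short-course arm or in either arm).

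| Accrual | Stop at true 5% | Stop at true 8% |
|---|---|---|
| Stated in the plan | 72% | 98% |
| 21 months | 17-30% | 68-82% |
| 27 months | 39-53% | 89-94% |
| 400/22 = 18.2 months | 10-20% | 52-72% |

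False stopping at a true 2% is about 1% or less for 21-27 months.

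**Step 5: sensitivity.**
- Weibull hazards with shape 0.7-1.5, accrual 21-27 months: 11-55% at 5% and 51-95% at 8%. With the clock at radiation start and this accrual, no scenario reaches 72% or 98%.
- Slower accrual of 33-36 months: 63-79% and 97-99%.
- Clock starting 4 months before radiation (the Appendix B limit from mastectomy without postoperative chemotherapy), with all the 18-month risk falling after radiation start: 41-58% and 90-96% for 21 months; 68-79% and 98-99% for 27 months.

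**The case against.** The strongest objection is the time origin. The 2% comes from a series of recurrence after mastectomy, and the 18-month definition in Section 9.1 belongs to questionnaires and photographs, not to this benchmark. Appendix B times radiation after postoperative chemotherapy from the last cycle, so the gap from mastectomy can exceed 4 months. With an assumed 6-month gap and all the risk after radiation start, the rule gives 59-71% at 5% for 21-month accrual and 84-89% for 27 months. With 8 months it gives 79-88% and 94-97%, and false stops at 2% become the problem (3-7% and 12-16%).

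This stands as a reason to make the size conditional. It does not rescue the stated figures. It requires the whole 18-month risk to be compressed into the period after radiation start; with a constant hazard from mastectomy, the hazard after radiation, and so the shortfall, is unchanged. The plan also states no such origin.

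Three further points are fair:
- How 72% and 98% were derived is inferred from the match in Step 2, because the plan does not show the calculation. The sentence on 5% also gives no time point.
- The rule's action is to suspend accrual, which has no force once accrual has closed.
- The DSMB goes on meeting every 6 months and may see the recurrence rate (Section 11.1), and recurrences are reportable for 3 years from radiation start (Section 7.2). These limit the harm, but neither carries a numerical criterion after the last radiation.

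**Conclusion.** The concern holds. The statistic and the benchmark refer to different lengths of follow-up, and that is visible from the text without simulation. The stated 72% and 98% are right for complete 18-month outcomes but are not the properties of the rule as written.

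On a clock from radiation start, with constant hazard, uniform accrual and 21-27 months of accrual, the rule stops in roughly a fifth to a half of trials at a true 5%. At 8% the shortfall is large with 21-month accrual (68-82%) and modest with 27-month accrual (89-94%). The size depends on accrual speed, hazard shape and the unstated time origin; accrual of 33-36 months or some mastectomy-based clocks would close or reverse it. Because a safety boundary's performance is misstated and the minimum correction costs almost nothing, this must be fixed.

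**What to change.** **Minimum.** State when the 18 months start (radiation start would match Section 9.1). Replace 72% and 98% with probabilities simulated for the rule actually used, under stated accrual, look times and hazard. This costs only wording and a simulation.

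**Preferable in addition, both parts together.**
1. Keep a check that acts during accrual. This can be the present crude rule up to last radiation. Alternatively, at looks before accrual closes, compare observed recurrences with (−ln 0.98/18) = 0.00112 per person-month, each patient capped at 18 months (exact Poisson, P < 0.025; assumes constant hazard).
2. Add 6-monthly looks until the last short-course patient reaches 18 months. At these looks, apply the existing boundary only to patients whose clock started at least 18 months earlier, whether or not they have recurred, and count only recurrences within 18 months.

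Under constant hazard from radiation start:

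| Part 2 combined with | Flag at 5% | Flag at 8% | False flag at 2% |
|---|---|---|---|
| Crude early check | 71-75% | 98-99% | 3-5% |
| Person-time early check | 72-74% | 98-99% | 5-6% |

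Across Weibull shapes 0.7-1.5, false flags are 3-5% and 4-9% respectively.

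**Cost.** About four more DSMB looks at data already reportable. False flags rise from about 1% or less, and many flags arrive after accrual closes, when they prompt DSMB review and not suspension. Flags before accrual closes at a true 8% (21-month; 27-month accrual) are 23-29%; 62-70% with the crude check and 68-76%; 82-87% with the person-time check. The present rule gives 23-29%; 56-66%.

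**Two changes to avoid.** Part 2 alone would flag before accrual closes at a true 8% in 0% (21 months) or 34-38% (27 months) of trials. Simply running the crude rule until 18 months after the last radiation start would give about 18-29% false flags at a true 2% (10-66% across hazard shapes), because late events count against an 18-month limit.

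As a secondary point, state how patients withdrawn at distant recurrence (Sections 7.2 and 8) enter the numerator and denominator.

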5. REGISTRATION AND RANDOMIZATION PROCEDURES

5.1 Registration Process for all sites

This section applies to DF/HCC Institutions (Dana-Farber/Harvard Cancer Center) and all other investigative sites.

To register a participant on the FABREC Trial, please follow these steps:

- Each participating site should identify eligible participants at their site.
- The consenting investigator should approach the patient and hold an informed consent discussion.

- If the potential participant agrees to participate, the consenting investigator and the patient should both sign the Informed Consent document.
- The study staff should then send the following documents to the Central Study Coordinator (CSC) via secure email to [contact] or via fax to [contact] (be sure to write ATTENTION: FABREC Central Study Coordinator on your fax cover sheet).
 1. Signed Informed Consent Form (all pages)
 2. Signed HIPAA authorization form (if applicable: At some sites the HIPAA authorization form and the informed consent document are two separate documents. At other sites, the HIPAA authorization form is contained within the informed consent document, so only the informed consent document need be submitted)
 3. Completed Eligibility Checklist
- The CSC will review the eligibility checklist to ensure that all fields are complete and that all values are within the acceptable range allowed by the protocol. If any information is missing, the CSC will contact the site.
- Next the CSC will work with the Dana-Farber Office of Data Quality (ODQ) to register and randomize the participant.
- Within 24 business hours*, the CSC will email the following information to the site:
 1. Confirmation that the participant has been successfully registered
 2. The participant's unique study ID number
 3. The arm to which the participant was randomized

*Business hours for this study are defined as: Monday through Friday from 8:00 AM to 5:00 PM Eastern Time, not including holidays.

If you need expedited assistance during normal business hours (Eastern Standard Time), please contact the FABREC Central Study Coordinator at [contact] or [contact].

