5.2 Study Enrollment Timing

REGISTRATION: Participant must be registered and randomized before protocol treatment (PMRT) begins.

BASELINE PATIENT QUESTIONNAIRE: The baseline questionnaire can be administered to the patient immediately following signed consent (**recommended**). The baseline questionnaire must be completed by the participant after she signs informed consent but before PMRT begins.

[figure not shown]
TREATMENT: Protocol treatment (PMRT) must begin ≤ 4 -months after randomization. Issues that would cause treatment delays should be discussed with the Study Chairs. Permission to deviate from DF/HCC SOP REGIST-101A has been approved and is documented in OnCore.

The rationale for allowing ≤ 4 months between randomization and start of PMRT is that there are a lot of treatment-related activities that must occur between Arm Assignment and PMRT

Initiation including: chemotherapy must be completed (as/if applicable); sequential inflations of the tissue expander need to be completed (as/if applicable); simulation must be performed locally at the treating site; the physics plan must be generated and approved locally at the treating site; and treatment verification films need to be approved locally at the treating site.

Note: the sponsor does not need to pre-approve your PMRT plan.

Information about PMRT treatment planning will be collected via Medical Record Review CRFs. The PMRT Treatment Plan for a patient does **not** need to be submitted prior to initiation of PMRT; this will reduce study burden on sites and clinicians.

Note: Concurrent systemic therapy will be considered on a case-by-case basis. Please ask the study co-chairs about whether any systemic therapy may be administered concurrently with PMRT.

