6.2 Radiation technical factors

- Radiation will be delivered with megavoltage (MV) equipment at energies of 6MV or higher.
- Protons are not permitted.
- Bolus to the mastectomy scar or chest wall will be prescribed at the discretion of the treating physician.
- No boost dose to the scar or other areas of the reconstructed chest wall is permitted.
- No deflation or expansion of tissue expander(s) should occur between simulation and radiation treatment completion.

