8. SCHEDULE OF ASSESSMENTS

	Prior to Enrollment (Screening)	Baseline (After participant signs informed consent)	During Radiation Therapy (both arms)	30 Days after RT completion	6 mos. +/- 4 weeks after RT initiation	12 mos. +/- 4 weeks after RT initiation	18 mos. +/- 4 weeks after RT initiation	Every year for 10 years after RT initiation
Medical chart review	X	X		X		X		X
SAE Reporting			Reportable SAEs that occur at any time between initiation of PMRT and 3-years after the initiation of PMRT must be submitted via InForm (see AE section).					
Radiation Treatment Information				X				
Photo Evaluation		X			X	X	X	
Participant Questionnaires		X			X	X	X	
Annual Follow-Up								X

Medical Chart Review. Medical Record Review CRFs will collect data on sociodemographic information, social history, cancer diagnoses, co-morbidities, treatment details, radiation treatment, surgical history and follow up, toxicities, medical history and follow up, disease recurrence, significant clinical events, and mortality.

Study Visits. Because this is a pragmatic trial, there are no protocol mandated study visits. All clinic visits are per standard of care.

Solicited AEs and Expedited SAE Reporting. See Adverse Event Reporting section of protocol for full details.

Radiation Treatment Information. Sites will enter specific information related to the radiation treatment received. This information will be collected by reviewing participants' medical charts at the end of treatment.

Photo evaluation. In order to assess reconstruction, de-identified photos of participant reconstruction will be submitted for evaluation by the Study Chairs or delegate. The participant may take and submit the reconstruction photographs herself (see appendix for patient-facing instructions on how to take and submit reconstruction photographs), or any clinician (nurse, doctor, etc.) who has been trained on the FABREC protocol may take reconstruction photographs.

In extremely rare cases where submission of photographs is not possible, the study chairs will work with the site investigator to complete the Cosmetic Outcome CRFs.

Participant Questionnaires. The following contain items from the following instruments:

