In addition to age stratification (see 10a and 10b), heterogeneity or variation in outcomes will be examined based on pre-specified patient, cancer and treatment-related attributes (“**Table: Pre-specified attributes to examine heterogeneity/patient subgroups**”). These factors are included because they may have an independent association with the outcomes examined. As shown in the power considerations for Objective 1, with our sample size we will have a sufficient power to detect heterogeneity of treatment effect. We will not adjust for the multiplicity of the statistical testing, because the goal of the HTE analyses is not to confirm a specific treatment heterogeneity hypothesis, but to generate hypotheses of potential treatment

heterogeneity. Towards this end, we will focus more on describing the estimated treatment differences in each of pre-specified subgroups than testing.

We have also planned analyses to identify subgroups of patients in which the treatment effect (benefit of short-course therapy) is potentially more pronounced than the average treatment effect, using a multivariable scoring approach.⁵⁵ Specifically, we will derive a multivariable model that predicts the treatment difference for each patient. Based on the predicted treatment difference scores, we will be able to define subgroups or clusters of patients who benefit more from short-course radiation therapy than the average patient on the study. For example, we will make two subgroups: one which consists of patients only with positive predicted treatment differences, and the other which consists of the remaining patients with negative predicted treatment difference. We will estimate the average treatment difference in each of the two subgroups and also perform a test for interaction.

Table: Pre-specified attributes to examine heterogeneity/patient subgroups	
Patient attributes:	Age (younger than 45, 45 and above) Smoking status Body mass index Comorbidity (hypertension, diabetes) Mastectomy specimen weight
Cancer attributes:	Tumor type (ductal, lobular, mixed histology) Tumor size Receptor status Tumor grade
Treatment attributes:	Number of nodes removed Expander versus permanent implant Volume of implant/expander fill Chemotherapy (yes/no) and regimen and timing of chemo Hormonal therapy Radiation therapy fields Bolus regimen Use of acellular dermal matrix Mastectomy scar location Use of biologic therapy

10f. AE Monitoring

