- 2) Supraclavicular (+/- axillary) nodes: Anterior-posterior fields as required to achieve dose homogeneity (see “Treatment planning requirements” below). Typical medial and superior borders are the pedicle and top of first rib, respectively. The inferior border will be matched to the superior border of the tangential fields as per institutional protocol. The lateral border will be set by the treating physician. Blocks (e.g., spinal cord, humeral head) may be utilized.

Treatment planning requirements.

- 1) Megavoltage (6 MV or above) is required. CT simulation will permit generation of a 3D conformal or IMRT plan.
- 2) Coverage of the planning target volumes by isodose curves will be as per the treating physician discretion. The only coverage stipulation is 95% coverage at the rib-lung interface.

Other coverage decisions are at the discretion of the treating physician, to allow for clinical judgment to address different clinical scenarios, and to optimize the generalizability of the results of this pragmatic trial.

3) The maximum dose inhomogeneity permitted is 110% for the lymph nodes and 110% (with less than 1 cc > 110%) for the chest wall. Lightly-weighted oblique subfields are permitted.

Note: There is no specified maximum dose on the composite plan. The composite plan may exceed 110%. Individual plans for the chest wall and lymph nodes must not exceed 110% inhomogeneity.

4) Mean cardiac dose and V20 (volume of ipsilateral lung receiving 20 Gy) will be recorded.

5) Inclusion of IMNs will be recorded.

6) The metal port in the tissue expander should be accounted for in the planning process, and if possible, the correct density used.

7) Bolus to the mastectomy scar or chest wall may be prescribed at the discretion of the treating physician (specifics will be recorded at the time of patient registration).

Treatment verification and quality assurance.

1) Machine verification films are required on or prior to the first treatment day, and at least once a week during treatment or as per institutional protocol.

2) The radiation therapy “chart” will be reviewed by the physics staff as per institutional protocol, to evaluate for discrepancies in documentation, dose prescription and dose recording.

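### Section 10e uses radiation fields and expander fill as treatment-effect subgroup factors although both can be settled after the arm is known, and it does not say which bolus value it uses

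*Combined protocol and SAP*

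**What the plan says.** Section 10e lists patient, cancer and treatment attributes for examining variation in the treatment effect. The treatment attributes include "Volume of implant/expander fill" and, in sequence, "Hormonal therapy Radiation therapy fields Bolus regimen", together with chemotherapy (with regimen and timing) and biologic therapy. No attribute carries a time of measurement. The section describes the analyses as hypothesis-generating, puts the weight on describing subgroup treatment differences, and adds a multivariable score to find patients who benefit more than average from the short course.

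The order of events is set elsewhere:

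- **Section 5.1.** After the registration papers arrive, the site is emailed "The arm to which the participant was randomized". No masking of the treating physician is described.
- **Section 5.2.** Radiation may start up to 4 months after randomisation because "there are a lot of treatment-related activities that must occur between Arm Assignment and PMRT" initiation. Among these, "sequential inflations of the tissue expander need to be completed (as/if applicable); simulation must be performed locally at the treating site"; chemotherapy completion (where applicable) and the physics plan are also listed.
- **Section 6.2.** Expander volume is held constant only from simulation onward. On bolus: "Bolus to the mastectomy scar or chest wall will be prescribed at the discretion of the treating physician". No time is given.
- **Section 6.4.** Nodal targets are left to the physician. A 107% inhomogeneity aim is set for hypofractionated cases only, with 110% permitted.
- **Appendix B, planning item 7.** For bolus, "specifics will be recorded at the time of patient registration".
- **Section 8.** On details of the radiation received: "This information will be collected by reviewing participants' medical charts at the end of treatment".

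**The concern.** A subgroup treatment effect inherits the protection of randomisation when the subgroup is defined by something the arm cannot have influenced. Fields are planned, and unfinished expanders are filled, by clinicians who may know whether the patient will receive 200 or 266 cGy per fraction. If that knowledge changes who gets a nodal field or how far an expander is filled, patients with the attribute in one arm differ in prognosis from patients with it in the other. The subgroup difference then mixes selection with treatment effect.

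The subgroup estimates are the main product of section 10e, and labelling an analysis hypothesis-generating does not remove selection bias. The benefit score has a further problem: a predictor settled after allocation may be distorted by the arm, and its value is not available when the fractionation schedule is being chosen, which is when such a score would be used.

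**Working it through.** **1. When each factor is settled.**

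| Factor in section 10e | Timing in the documents | Status |
|---|---|---|
| Radiation fields | Simulation and physics plan after arm assignment (5.2); nodal targets at physician discretion (6.4) | Planned with the arm known |
| Expander fill, inflation incomplete | Inflation completed after assignment (5.2); held only from simulation (6.2) | Final value settled with the arm known |
| Permanent implant, or expander already full | Enrolment follows reconstruction (section 4) | Settled before randomisation |
| Bolus | Recorded at registration (Appendix B); treatment received abstracted at end of treatment (section 8) | Value used in 10e not stated |
| Chemotherapy timing, hormonal and biologic therapy | Chemotherapy completed after assignment where applicable (5.2); 5.2 does not address the other two | Open where not settled at randomisation |
| Nodes removed, expander versus implant, acellular dermal matrix, scar location | Surgery, with enrolment afterwards (section 4) | No issue |

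**2. The plan's own figures for heterogeneity.** Section 10e relies on the age-interaction power in section 10b: effects 4.0 and 2.0, hence an interaction of 2.0, with 40% of 200 per arm younger (80 younger, 120 older).

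Power = Φ(2.0/SE − 1.96), where SE = SD × √(2/80 + 2/120) = SD × 0.2041.

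- SD 3.5: SE 0.714, power 0.799 (table 0.80)
- SD 4.0: SE 0.816, power 0.688 (table 0.69)
- SD 4.5: SE 0.919, power 0.586 (table 0.59)

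The table reproduces. It concerns age, a stratification factor fixed before randomisation, and does not bear on factors settled later.

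**3. Illustration of bias.** SD 4.0 is from section 10b. The documents give no shares or correlations, so everything else here is an assumption. The true treatment effect is 0. U is a standard normal prognostic score with correlation R (0.3 to 0.5) to PWB change. A patient has the attribute when c·U + √(1−c²)·noise exceeds a cut-off, with c from 0.3 to 0.8. The cut-off gives share q in that arm.

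Mean U among those with the attribute = c × φ(t)/q, with t = Φ⁻¹(1−q). The ratio φ(t)/q is 1.159, 0.966, 0.798 and 0.497 at q = 0.3, 0.4, 0.5 and 0.7.

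False difference = 4.0 × R × c × (ratio in short − ratio in long).

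| Share short / long | Difference in ratio | Lowest (R 0.3, c 0.3) | Highest (R 0.5, c 0.8) |
|---|---|---|---|
| 50% / 50%, same rule | 0 | 0 | 0 |
| 40% / 50% | 0.168 | 0.06 | 0.27 |
| 30% / 50% | 0.361 | 0.13 | 0.58 |
| 30% / 70% | 0.662 | 0.24 | 1.06 |

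At 30%/70% the complementary subgroup shows the same false difference with the same sign, so both subgroup estimates are biased while the interaction is not.

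The interaction is biased when the rules differ. Suppose shares are 50% in both arms but only one arm selects on U, with c from 0.3 to 0.5. The bias per subgroup is 4.0 × R × c × 0.798 = 0.29 to 0.80, with opposite signs in the two subgroups. The interaction bias is twice that, 0.57 to 1.6, against the planned interaction of 2.0.

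**4. Scale.** At 40%/50% the subgroup has 80 and 100 patients, with SE 4.0 × √(1/80 + 1/100) = 0.60. At 30%/70% it has 60 and 140, with SE 4.0 × √(1/60 + 1/140) = 0.62. The false difference therefore runs from about 0.1 SE (0.06/0.60) to 1.7 SE (1.06/0.62). Section 10b cites a change of 2 points as clinically meaningful.

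**The case against.** Section 10e is openly exploratory, the primary comparison is untouched, and no passage shows that the arm drives fields, fill or bolus. If physicians apply the same rule in both arms, the bias is zero. Intended fields recorded at registration could precede simulation by months, and fill at registration may not be the fill irradiated, so a pre-arm definition gives up some clinical relevance. All of this stands. It limits the severity but does not supply the missing rule, and the inhomogeneity aim in section 6.4 shows that planning is not wholly indifferent to arm.

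A reader might go further in four ways that the documents do not support:

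- **That bolus is fixed after the arm is known.** Appendix B has its specifics recorded at registration. The eligibility checklist is not reproduced, and since bolus appears among the inclusion criteria (3.1, item 5), the checklist may carry it. Against that, section 5.2 says planning information comes through Medical Record Review forms, and section 9.1 places the baseline one after enrolment. The recording time is unresolved, and nothing ties section 10e to either value.
- **That these subgroup contrasts are not randomised comparisons.** That is too absolute. What is lost is the guarantee of comparability.
- **That every treatment attribute is affected.** Those settled at surgery are not.
- **That the trial could not detect an arm difference in bolus.** Section 8 collects the treatment received, so it could be tabulated by arm.

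**Conclusion.** The point holds for radiation fields, and for expander fill in patients whose inflation is incomplete at randomisation. For bolus it is an inconsistency: sections 6.2, 8 and 10e and Appendix B must be reconciled on which value is analysed. The same timing question applies to chemotherapy timing, hormonal therapy and biologic therapy where these are not settled at randomisation.

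The figures show that the problem can range from nothing to about 1.1 PWB points per subgroup when shares differ and selection is imperfect. They rest on assumed shares, R and c and are not a prediction. With noise-free selection on prognosis (c = 1) the 30%/70% case would reach 0.79 to 1.32, which is best read as a ceiling for that case. Severity is low to moderate: a cheap improvement to exploratory analyses.

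**What to change.** 1. **Section 10e.** State that treatment-effect subgroups and benefit-score predictors are defined only by values recorded before the arm is released to the site.
2. **Eligibility checklist.** Add intended bolus, intended fields, and systemic therapy given and planned, completed before the Central Study Coordinator sends the arm.
3. **No pre-arm value available.** This covers final expander fill and patients already randomised whose intention was not recorded. Label the factor post-randomisation, tabulate it by arm descriptively, and leave it out of the subgroup treatment effects and the benefit score.
4. **Bolus.** Reconcile Appendix B item 7 with sections 6.2 and 8, so that the recorded intention and the treatment received are separate items with stated times, and name in section 10e the one that is used.

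Attributes settled at surgery need no change, and physician discretion over bolus and fields is unaffected. The cost is a few checklist lines, a sentence or two in section 10e and a reworded appendix item. The downside is that these subgroups will reflect intention, which may differ from the treatment delivered.
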